6.10 Diversity Supplement - Withdrawal from Study

Parents may withdraw their child from participation in the telephone follow-up. We will not contact the family to collect new information about their child if they opt out or ask to withdraw from the telephone follow-up. However, we will use information obtained through prospective observational methods (see 4 in parent grant) and retrospective chart review as these activities are covered under waiver of informed consent. There are no

penalties nor benefits lost to the patient if the legal guardian decides to withdraw their child's data.

6.11 Diversity Supplement - Data Analysis

This study has two methodologies for data analysis based upon the specific aims.

- Specific Aim 1. Determine social factors associated with pediatric CSI risk using census tract data from the American Community Survey and other geographic data.

Standard descriptive summaries (e.g. means and standard deviations for continuous variables such as age and percentage for categorical variables such as gender) will be used to summarize demographic variables. To analyze whether the distribution of social factors in the CSI population differs from that in the general population we will calculate a standardized incidence ratio based on population level data from the American Community Survey. The methodology compares the observed distribution of social factors in the study's CSI population to what would be expected in the general population based on a synthetic cohort from census data.

- Specific Aim 2. Determine social factors affecting disparities in health care delivery, post-injury care management, and functional outcomes in children with CSIs via structured interviews.

Univariate analysis using chi-square testing and multivariate logistic regression will be used to determine the association between social factors and inequities in healthcare delivery and functional outcome for children with CSI including school performance, accessibility of healthcare resources, ED visits, and unplanned readmissions.

6.12 Diversity Supplement - Consent Procedures

This study has two methodologies for consent procedures based upon the specific aims.

Aim 1. Medical Record Review Waiver of Consent Process

We are requesting a waiver of consent based on the following qualifications: the research is limited to existing data; the data involves no more than minimal risk to the subject; waiver of consent will not adversely affect the rights and welfare of subjects,

and the research could not be practicably carried out without the waiver. The proposed study meets all regulatory requirements for a waiver, as outlined in the Code of Federal Regulations Title 45 Part 46, “Protection of Human Subjects”. Justification is provided below.

- See 45 C.F.R. 46.116 (d)(1) See [10.4](#) The research activity proposed in this application is retrospective chart review and minimal risk.
- See 45 C.F.R. 46.116 (d)(2) See [10.4](#) Beyond medical record review, there are no activities or interventions outside of routine clinical care. Nothing proposed in the research will adversely affect the rights and welfare of the subject.
- See 45 C.F.R. 46.116 (d)(3) See [10.4](#) The research proposed in this application would be impracticable to conduct if informed consent is required. Eligible subjects enrolled in our study are identified through the parent grant which currently operates with a waiver of informed consent. In addition, PHIS data sets are derived from over 45 hospitals throughout the United States; therefore, data collection and reporting would not be feasible if the waiver of HIPAA authorization was not carried out. We are requesting a waiver of HIPAA authorization based on the following qualifications: the use or disclosure of PHI involves no more than minimal risk, the research could not practicably be conducted without the waiver or alteration, and the research could not practicably be conducted without access to and use of PHI. The protected health information will not be reused or disclosed to any other person or entity, except as required by law or for authorized oversight of the research project.
- See 45 C.F.R. 46.116 (d)(4) See [10.4](#) The research activity proposed in this application is retrospective chart review, so no additional pertinent information will be provided to the subjects.

Aim 2. Telephone Follow-up Assessments Waiver of Written Documentation of Consent

We are requesting a waiver of written documentation of consent. The proposed study meets all regulatory requirements for a waiver, as outlined in the Code of Federal Regulations Title 45 Part 46, “Protection of Human Subjects”. Justification is provided below.

- **21 CFR 56.109(c)(1) and 45 C.F.R. 46.117 (c)(1)(ii) Research presents no more than minimal risk of harm to subjects and involves no procedures for which written consent is normally required outside of the research context.**

The research activity proposed in this application is a telephone interview which is a minimal risk activity. Beyond the interview, there are no activities or interventions outside of routine clinical care.

- See 45 C.F.R. 46.116 (d)(1) See [10.4](#) The research activity proposed in this application is retrospective chart review and minimal risk.
- See 45 C.F.R. 46.116 (d)(2) See [10.4](#) Beyond medical record review, there are no activities or interventions outside of routine clinical care. Nothing proposed in the research will adversely affect the rights and welfare of the subject.
- See 45 C.F.R. 46.116 (d)(3) See [10.4](#) The research proposed in this application would be impracticable to conduct if written informed consent is required as eligible subjects are recruited through a national, multi-center trial study across the country for telephone follow-up assessment.
- See 45 C.F.R. 46.116 (d)(4) See [10.4](#) Guardians of eligible children will be provided a Consent, Parental Permission, and Authorization Cover Letter from the DCC regarding the study. This handout will be mailed to the legal guardian's home address if the legal guardian is conversant in English or Spanish languages. A follow-up call will be made to the legal guardian. At the time of the phone call, [name] or RC will confirm that the legal guardian has received the cover letter and obtain verbal consent for the phone follow-up questions.

Figure [6](#) represents the proposed research activity and respective requested waivers of consent for the study population

7 Data Management

Tool Development and Evaluation Figure 2 on page 18 illustrates the iterative process of tool development and validation. This process relies on continuous monitoring of clinical data with interim analyses to model and evaluate potential decision rules in parallel with the Applied Cognitive Task Analysis which will inform the design of the Pediatric CSI Risk Assessment Tool prototypes. We will evaluate the study progress and data collection at multiple time points during the study collection period. The data analysis will use interim evaluations to measure progress towards achieving the study

specific aims. This process of refinement will use qualitative and quantitative methods to solicit input regarding the tool attributes from subject matter experts and clinical end-users, in particular practicing EMS, ED, and surgical personnel.

8.1 Specific Aim Analyses

Specific Aim 1. Develop the Pediatric CSI Risk Assessment Tool in children with blunt trauma using prospective observational data obtained from ED providers.

The first step in tool development is the refinement of the original PECARN model into a decision rule that has very high sensitivity for identifying CSI in children with blunt trauma and sufficient specificity to result in a meaningful reduction in the use of spinal precautions and radiographic imaging. To evaluate Aim 1 we will use the prospective observational data obtained from ED providers to refine a clinical decision support tool that has near perfect sensitivity (lower 95% confidence limit $>95\%$) and adequate specificity to reduce unnecessary interventions (lower 95% confidence limit $>40\%$) when screening children for CSIs. To develop the decision rule, we will use binary recursive partitioning on a study population consisting of approximately 13,333 subjects collected from eight PECARN sites.

We will use multiple analytic techniques to refine the decision rule that will serve as the basis for the Pediatric CSI Risk Assessment Tool. We will use both CART 7.0.0 (San Diego, CA) to perform recursive partitioning for the purpose of building a clinical decision tree and multivariable logistic regression modeling using SAS 9.4 (Cary, NC) to develop a risk model. This is important because each method will result in a tool that has different characteristics. As an example, we will use regression analysis if we determine that the optimal tool is a “risk calculator” in which a child's risk for CSI is calculated based on the child's individual constellation of findings and guidance for CSI evaluation (e.g. nothing versus plain radiographs versus CT) is set for various risk thresholds. We can use regression analysis, as was performed in our pilot work, to determine a set of variables that has sufficient performance characteristics for use as a simple tool in which the presence of any one finding would identify the child as at non-negligible risk for CSI and therefore requiring further evaluation.^{90, 94, 95} Recursive partitioning results in a clinical decision tree in which the resultant tool is a patient care algorithm, with each terminus resulting in a risk estimate on which we base clinical decisions regarding CSI evaluation.^{96, 97} Our ACTA will help determine which type of tool and therefore which analytic techniques for decision rule refinement will be most useful for tool design. It may be that ultimate implementation requires multiple different tools based on various patient scenarios which differ by parameters such as setting, provider type, point of entry into the health care system, and timing within the patient's clinical course.

Using the results of our ACTA, we will develop conceptual prototypes of the Pediatric CSI Risk Assessment Tool suitable for user testing. We will perform a series of iterative formative usability tests to evaluate the tool prototypes.¹¹⁸⁻¹²⁰ Prototype assessment will be scenario-based and designed to address the various clinical roles and workflows. At each iterative testing period, we will assess the prototypes in terms of usability, utility and effectiveness, but also in supporting the desired outcome of the decision rule. We will modify the prototypes, or if necessary redesign and retest to address the results. With each iteration, the prototypes will increase in the level of detail and functionality they represent. The development and user testing of conceptual system prototypes is well-established in general usability science and moreover in the development of health information technology solutions.^{103, 104, 118, 121, 122} Team members have experience using dedicated software, such as Axure (Axure Software Solutions, San Diego, CA) to support rapid, interactive prototyping of clinical decision support systems suitable for user testing.¹²³⁻¹²⁶

We will include all children that present to the study site EDs, regardless of point of entry into the health care system. While this is important in terms of building a tool that is representative of the full spectrum of children with CSI, this has the potential for resulting in ascertainment bias on the part of the ED providers responding to the assessment forms. In order to address this potential bias, we will determine the operating characteristics of our prediction tool for the entire cohort as well as key sub-samples of children, including those without cervical spine imaging prior to presentation at the study site, those who do not have a trauma team activation, those who arrive via scene response EMS, and those who arrive via private motor vehicle. For any subgroup with poor performance, we will conduct an exploratory analysis by deriving separate rules. As a standard quality measure for observational studies such as this, we will compare the demographic characteristics of enrolled children to those that were eligible and not enrolled.

In addition, when conducting our analyses, we will examine the operating characteristics of the prediction rule for several high-risk groups including young children (<8 years), children with injuries that require either surgical stabilization or stabilization with an orthotic device for >30 days, children with medical conditions that predispose to CSIs and children who are victims of abusive trauma. For any high-risk group with poor performance, we will conduct an exploratory analysis by deriving separate rules.

While every effort will be made to ensure data quality, we will conduct several analyses to assess the effect of the quality of the data. CART automatically selects surrogate variables in the event that a splitting variable has a missing or unknown value. For regression modeling, we will use multiple imputations to allow for inclusion of records where the provider failed to assess the patient for the clinical finding. Further, if a risk factor in the tool has low prevalence or poor kappa for EMS-ED and ED-Surgical

provider paired observations(lower 95% confidence interval <0.4), the analyses will be re-run excluding the variables for comparison.

Specific Aim 2. Validate the Pediatric CSI Risk Assessment Tool in a separate population of children with blunt trauma using prospective observational data obtained from ED providers.

To validate the Pediatric CSI Risk Assessment Tool, we hypothesized that the Pediatric CSI Risk Assessment Tool will retain adequate sensitivity (lower 95% confidence limit $>95\%$) and specificity (lower 95% confidence limit $>40\%$) in an independent sample of children presenting for to the ED evaluation following blunt trauma. To evaluate this aim, we will enroll patients from PECARN sites not involved in enrollment for Specific Aim 1. Using a population of 8,889 collected from the prime site and an additional seven different PECARN sites and the prime, we will report standard performance measures to describe the accuracy of the rule: sensitivity, specificity, positive predictive value, negative predictive value, and positive and negative likelihood ratios. We will also report 95% CIs for all above measures. In addition to evaluating the validity of the decision rule, we will continue to perform and report formative testing on the Pediatric CSI Risk Assessment Tool prototypes. If performance of the rule or provider acceptance is low at our interim analysis, we will return to the training set in Aim 1 and approach refining the decision rule using a different process and revalidate. We will report the demographic characteristics of the validation study cohort using means and medians as appropriate for continuous measures and frequencies and percentages for categorical measures.

Specific Aim 3. Validate the Pediatric CSI Risk Assessment Tool in a population of children with blunt trauma using prospective observational data obtained from EMS providers.

Using a set of patients who have data from both EMS and ED providers collected throughout the both the derivation and validation phases of the study we will evaluate the performance of the rule using EMS variables. Additionally, we will assess agreement between EMS and ED providers using the kappa statistics. It is expected that there will be a minimum of 7,444 subjects with data from both EMS and ED providers available for this aim. As in Aims 1 and 2 we will report the decision rules performance based on standard measures: sensitivity, specificity, positive predictive value, negative predictive value, and positive and negative likelihood ratios. We will also report 95% CIs for all above measures. If performance of the rule derived in Aim 1 is poor we will derive an EMS specific rule using similar methods described above.

9 Study Training

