[name] et al. will conduct this work at approximately 18 PECARN trauma centers and collect prospective observational data from EMS and ED providers regarding CSI risk factors for children who undergo emergency evaluation after blunt trauma and follow enrolled subjects for 28 days to determine CSI status. The study will occur in two phases: development (13,333 children; 240 children with CSI) and validation (8,889 children; 160 children with CSI). The study will also capitalize on the research infrastructure to conduct an Applied Cognitive Task Analysis (ACTA) and tool prototype testing that will inform the iterative tool design to ensure that the tool is useable by EMS and ED providers. With data from the development cohort, a useable clinical decision support tool will be constructed that achieves > 95% sensitivity, as well as adequate specificity (> 40%) in the prediction of CSI. Subsequently, [name] et al. will determine the performance characteristics of the tool in the independent validation cohort and in a cohort that has EMS provider observations. The ultimate output from this project will be a set of specifications for the Pediatric CSI Risk Assessment Tool that will include a validated clinical decision rule, validated tool designs and functions, and recommendations for implementation. An accurate, validated, and ultimately field-tested Pediatric CSI Risk Assessment Tool will safely limit unnecessary spinal precautions and radiographic testing for millions of children while helping identify those children who are truly at risk for CSI.

1 Study Summary

Cervical spine injuries (CSI) are serious, but rare events in children.^{1, 2} Spinal precautions (rigid cervical collar and immobilization on a longboard) in the prehospital setting

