2.2 Preliminary Studies

With federal funding, Pediatric Emergency Care Applied Research Network (PECARN) investigators, led by this study's Principal Investigator (PI), conducted a large retrospective case-control study of children with CSI which allowed us to identify a set of risk factors that are significantly associated with CSI.^{90, 91} These factors; altered mental status, focal neurological deficits, self-report of neck pain, torticollis, substantial injury to the torso, predisposing condition, high-risk motor vehicle crash, and diving mechanism; had greater than 98% sensitivity for identifying all children with CSI in the cohort. If these mechanistic and clinical factors were used as clinical screening criteria for CSI, radiographic imaging for CSI in the cohort would have been reduced by more than 25%. These factors, however, need prospective evaluation and refinement prior to implementation as a risk assessment tool that guides management. In order to develop a risk assessment tool for CSI in children, a large prospective cohort of children experiencing blunt trauma is required due to the rarity of CSI.

As a prerequisite for a large, prospective multi-center study to develop and validate a Pediatric CSI Risk Assessment Tool, we conducted a NICHD R21-funded, 4-center (Washington University in St. Louis, Medical College of Wisconsin, Cincinnati Children's Hospital Medical Center and Nationwide Children's Hospital) pilot study aimed at developing the infrastructure (materials, methods and procedures) necessary for collecting prospective data from prehospital EMS providers and ED providers who care for children after blunt trauma.⁹² We developed a web-based, branch-logic questionnaire using Research Electronic Data Capture (REDCap) that was administered via a tablet computer to ED providers (attending or fellow pediatric emergency medicine, emergency medicine or hospitalist physicians, or advanced practice nurses or physician assistants) during their ED evaluation of children with blunt trauma, and if applicable, to the EMS providers who had rendered scene response care.^{92, 93} The questionnaire assessed factors determined a priori to be associated with CSI in children, including those from our retrospective case-control study.^{69, 73, 90, 91, 94, 95} We collected data in the ED under waiver of informed consent;

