however we provided parents/guardians a study information sheet with instructions for withdrawal from further phone follow-up.^{92, 96-99} For children who had cervical spine imaging, we determined presence of CSI by review of the imaging reports by the Site PI with verification of the CSI through review of the spine surgeon's consultation notes. For those children who did not undergo cervical spine imaging in the ED, we made telephone follow-up calls 21-28 days after the ED visit to confirm that the child was free of CSI. To determine whether or not our cohort was representative of all children meeting inclusion criteria, we reviewed daily ED census reports to identify missed eligible children and gathered a limited data set.

Preliminary results from this pilot study support the feasibility of conducting a larger investigation using these established methods. We enrolled 4091 children over 18 months; 84.9% of eligible subjects during enrollment hours and 70.9% of all eligible subjects.⁹² The characteristics of those children that we enrolled were comparable to those that were missed.⁹² We captured the EMS provider's observations 60.2% of the time for those that arrived as a scene response. Importantly, there were 74 children within the cohort ultimately diagnosed with CSI (1.1 injuries per site per month; CSI incidence of 1.8%).⁹²

Table 1 on the next page demonstrates the prospective performance of our retrospectively-identified risk factors in identifying all children with CSI.^{94, 95} For each candidate risk factor, we calculated bivariable relative risks. We explored the PECARN model for CSI as a predictor set and considered children with at least one positive risk factor test positive for CSI risk. The PECARN model risk factors were 90.5% sensitive and 45.6% specific for CSI in the cohort. Retrospective medical record review of the 7 children missed by the PECARN model revealed that all either had a PECARN model risk factor that was not captured in the observational data (n=6; altered mental status and complaint of neck pain) and/or had one of the other observed candidate risk factors (n=5; axial load biomechanics, loss of consciousness, other signs of substantial head injury- skull fracture, upper thoracic tenderness and pain). These findings confirm our previously-identified risk factors for CSI in children.

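### Aim 1's sensitivity limit is read on the same children used to choose the rule, so it overstates performance; Aim 2 largely protects the final claim

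*Protocol*

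**What the plan says.** Section 8.1, Specific Aim 1, names the data and the criterion together: "To evaluate Aim 1 we will use the prospective observational data obtained from ED providers to refine a clinical decision support tool" with "near perfect sensitivity (lower 95% confidence limit" above 95%) and "adequate specificity to reduce unnecessary interventions (lower 95% confidence limit" above 40%). It then gives the method: "we will use binary recursive partitioning on a study population consisting of approximately 13,333 subjects collected from eight PECARN sites". The next paragraph adds logistic regression: "We will use multiple analytic techniques to refine the decision rule that will serve as the basis for the Pediatric CSI Risk Assessment Tool".

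The Abstract describes the same step, without confidence limits: "With data from the development cohort, a useable clinical decision support tool will be constructed that achieves" more than 95% sensitivity and more than 40% specificity. It expects 240 children with CSI among 13,333 in development and 160 among 8,889 in validation.

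Still under Aim 1, the rule's performance is to be examined in several subgroups and high-risk groups, and where it is poor, separate rules are to be derived as exploratory work. The Aim 1 text names no cross-validation, bootstrap or other correction for the search. Aim 2 applies the same two bars to an independent sample.

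**The concern.** A lower 95% confidence limit has its stated coverage when the rule was fixed before the data were seen. Here the rule is searched for on the data that supply the limit. Variables or splits can be added until few enough of the 240 injured children are missed, and some of that gain is chance. The limit then says less about new children than its label suggests.

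Three things depend on these figures before any validation: whether Aim 1 is reported as having met its sensitivity bar, which variables and splits are kept, and whether a subgroup is judged to perform poorly. Apparent performance can make a weak subgroup look acceptable. A rule that only appears to pass also meets a stricter miss allowance in the smaller Aim 2 cohort.

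**Working it through.** **Inputs.** CSI incidence 1.8% (74 of 4,091; section 2.2). Cohorts of 13,333 and 8,889 (Abstract). Bars: lower 95% limits above 95% and 40% (section 8.1).

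**Reproducing the plan's counts.** 13,333 × 0.018 = 239.99 and 8,889 × 0.018 = 160.00, which match 240 and 160. Children without CSI in development: 13,333 − 240 = 13,093.

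**Turning the sensitivity bar into misses** (two-sided 95% Clopper-Pearson):
- Development: 235/240 = 97.9%, lower limit 95.2% (passes). 234/240 = 97.5%, lower limit 94.6% (fails). At most 5 misses.
- Validation: 158/160 = 98.75%, lower limit 95.6% (passes). 157/160 = 98.1%, lower limit 94.6% (fails). At most 2 misses.

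Wilson limits allow the same counts. Wald limits allow 6 and 4.

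**What the bar protects against when the rule is fixed in advance.** P(misses ≤ 5 | n = 240) is 1.8% at true sensitivity 95%, 27.2% at 97% and 65.1% at 98%. These probabilities do not apply to a rule chosen on the same 240 children.

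**Specificity.** The lower limit exceeds 40% from 5,348/13,093 = 40.8%, so sampling error costs under one point. There is little room for chance gain.

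**Size of the optimism in sensitivity (illustrative).** The protocol does not give the number of candidate predictors, so these results rest on assumptions.
- Simulation A: 20 independent candidates with relative risks like those in Table 1 and assumed prevalences, greedy any-factor-positive rule, 60 development samples. Mean apparent minus true sensitivity was 1.5 points (5th to 95th percentile −0.1 to 3.4).
- Simulation B: 8 true predictors plus pure-noise predictors, greedy any-factor-positive rule, 300 runs each.

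| Noise predictors | Apparent sensitivity | True sensitivity | Optimism | Both Aim 1 bars met |
|---|---|---|---|---|
| 0 | 90.9% | 90.9% | 0.0 | 0% |
| 10 | 95.6% | 94.2% | 1.4 | 0% |
| 20 | 97.5% | 95.0% | 2.5 | 1% |
| 40 | 98.0% | 93.3% | 4.7 | 9% |

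In simulation B the optimism in specificity was at most 0.1 point in every row. No run that met both Aim 1 bars then met the Aim 2 sensitivity bar.

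**Carrying a just-passing rule into Aim 2.** With 5 misses in 240 the apparent miss rate is 5/240 = 2.08%.
- No optimism: P(misses ≤ 2 | n = 160, miss rate 2.08%) = 35%.
- With 1.5 points of optimism: miss rate 2.08% + 1.5% = 3.58%, and the probability is 7%.

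The difference between 35% and 7% is the effect of the optimism. The 35% itself reflects the limited precision of 160 cases.

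**The case against.** The strongest reply is that Aim 1 is development. Its bars can be read as a design target, and Aim 2 tests the same bars in other children. An overfitted rule should fail there, which is the purpose of a validation cohort. This stands for the final claim. It does not cover the Aim 1 claim itself, because section 8.1 says how Aim 1 is evaluated and states the bars as confidence limits.

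A second reply is that internal validation is usually specified in a statistical analysis plan, which was not available here. That is fair as to the method. The point made here concerns what the protocol does fix: the criterion and the data on which it is read.

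Four stronger readings are tempting and not supported:
- **Overfitting can easily carry a rule past both bars.** The specificity bar limits this: both bars were met in only 0% to 9% of runs in simulation B.
- **The pilot shows overfitting.** The retrospective factors "had greater than 98% sensitivity for identifying all children with CSI in the cohort", and later "The PECARN model risk factors were 90.5% sensitive and 45.6% specific for CSI in the cohort". But section 2.2 reports that 6 of the 7 missed children had a model factor that was not captured in the observational data. Counting those 6 as detected gives 73/74 = 98.6%, so data capture could explain nearly the whole fall. It should not be cited as evidence of overfitting.
- **The type of tool is chosen on these figures.** Section 8.1 says the applied cognitive task analysis (ACTA) helps determine the tool type, and separate subgroup rules are called exploratory.
- **Aim 3 repeats the fault.** Some of its children come from the derivation phase, but it scores the rule on EMS observations, not the ED observations used for fitting. That overlap is a separate matter.

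**Conclusion.** The point holds in limited form. The nominal 95% limit for sensitivity in Aim 1 lacks its coverage and is optimistic, because the rule is selected on the 240 injured children who supply it. Optimism in specificity is negligible. The amount for sensitivity cannot be fixed from the protocol. Roughly 1.5 to 5 points is an illustration that depends on the assumed number, prevalence and independence of candidate predictors, and it was zero when no noise predictors were offered.

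The consequence is confined to the Aim 1 sensitivity claim, the selection of variables and splits, and the reading of subgroup performance. A reader might infer that the study could end with a falsely validated rule. The documents do not support that, since Aim 2 applies the same bars to a separate cohort. That protection assumes the rule is locked before Aim 2 is analysed. The Aim 2 text allows a return to the training set after a poor interim result, which is why the locking should be stated.

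**What to change.** In section 8.1, Aim 1:
- Label figures from the development cohort as apparent performance.
- Judge the sensitivity bar, and poor performance in any subgroup, on cross-validated or bootstrap optimism-corrected estimates. The procedure should repeat the statistical selection of variables, splits and thresholds, for example leaving out one of the eight derivation sites at a time. The ACTA-driven choice of tool type need not be resampled.
- State that only the locked rule, applied to the Aim 2 cohort, decides whether the bars are met.

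No new data are needed. The cost is extra analysis time and slightly less favourable Aim 1 figures.
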